### **Concomitant medications**

All medications will be coded using WHO Drug, version 01Jun2009. The number and percentage of subjects using each concomitant medication will be summarized according to the WHO DRUG Class and preferred term (PT). Subjects with multiple uses of a concomitant medication will be counted once for a given WHO Drug Class and PT. Prior medications are defined as any medication with an end date before the first dose of study medication. Concomitant medications are defined as medications present on or after the first dose of study medication.

## **6. Statistical Methods**

### **6.1 General Methodology**

All statistical procedures will be performed using SAS Version 9.2 or higher.

Continuous variables, including those assessed on a discrete scale, will be summarized using descriptive statistics, including the number of subjects, mean, standard deviation, minimum, 25th percentile, median, 75th percentile, and maximum. For categorical variables, summaries will include counts of subjects and percentages.

### **Baseline**

Change in seizure related efficacy parameters will be calculated with reference to the baseline period defined as the baseline period (From Visit 1 to Visit 2) from protocol 093-045 and 093-046. The change in QOLIE, MADRS and safety parameters will be calculated with reference to the baseline as Day 0 (Visit 2) for protocol 093-045 and 093-046.

### **3-month visit windows**

There are four 3-month intervals for the 1-Year Open-Label Period. The first window is defined as  $\geq$ Visit 1 and  $<$ Visit 4, the second window is  $\geq$ Visit 4 and  $<$ Visit 5, the third window is  $\geq$ Visit 5 and  $<$ Visit 6 and the fourth window is  $\geq$ Visit 6 and  $<$ Visit 7). This 3-month interval will be used to summarize seizure related efficacy data.

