**2. Seizure frequency**

Seizure frequency from the subject’s diary data will be evaluated by standardizing the sum of seizures to a frequency per 4 weeks (28 days). The standardized seizure frequency (SSF) for any given period (including baseline) will be calculated as:

$$\frac{\text{Total number of seizures reported in the diary during the interval of interest}}{\text{Number of days on study for the interval of interest}} \times 28 \text{ days}$$

The number of days on study for the interval of interest will be determined by:

$$\text{Visit Date of last visit during the interval of interest} - \text{Visit Date of first visit during the interval of interest}$$

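### For the four 3-month windows, the SAP's window bounds and its days-on-study formula cannot be applied together: the literal SSF denominator is about 1 month in window 1 and zero in windows 2 to 4

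*SAP*

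**What the plan says.** SAP section 6.1, under the 3-month visit windows, states: "There are four 3-month intervals for the 1-Year Open-Label Period". Each window includes its opening visit and excludes its closing visit: Visit 1 to before Visit 4, Visit 4 to before Visit 5, Visit 5 to before Visit 6, and Visit 6 to before Visit 7. On their use it says: "This 3-month interval will be used to summarize seizure related efficacy data".

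Section 5.2.2, item 2, defines SSF as the diary seizure count in the interval, divided by "Number of days on study for the interval of interest", times 28. That divisor is a subtraction: "Visit Date of last visit during the interval of interest", minus the date of the first visit during the same interval. No day is added.

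The Schedule of Evaluations (section 5.1) puts Visits 1 to 7 at Day 0, Week 1 and Months 1, 3, 6, 9 and 12.

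Section 6.2 drops days without diary data from the SSF calculation and bases a dropout's last interval on the data available before dropout. It does not say which date ends a window.

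**The concern.** If the closing visit is outside the window, it cannot be the last visit during the window. The denominator then stops at the last visit inside, while the numerator still counts every seizure dated up to the closing visit. Numerator and denominator cover different spans.

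Windowed SSF feeds the percent change from baseline and its categories, the responder rate and SSF by seizure type (section 5.2.2, items 2 to 4 and 6). It also feeds the matching summaries in section 7.6 and the subgroup summaries in section 6.5. These address the secondary objective of maintained effect. The responder rate divides by all ITT subjects entering the period, so a subject whose SSF is undefined would stay in that denominator with no classification. Seizure-free status does not use days on study and is not touched.

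**Working it through.** **Inputs.** Window bounds: SAP 6.1. Denominator rule: SAP 5.2.2, item 2. Visit timing: SAP 5.1. The SAP gives visits in months, so the month length m is assumed: 28, 30 or 30.44 days. Subjects are assumed to attend scheduled visits only, on schedule.

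**The plan's own figure.** Each window is labelled 3 months, that is 3m = 84, 90 or 91.3 days.

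**Applying both rules as written.**

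| Window | Scheduled visits inside | Last minus first visit inside | Closing minus opening visit |
|---|---|---|---|
| 1 | 1, 2, 3 | Visit 3 − Visit 1 = m (28 / 30 / 30.4 days) | Visit 4 − Visit 1 = 3m (84 / 90 / 91.3 days) |
| 2 | 4 | 0 | Visit 5 − Visit 4 = 3m |
| 3 | 5 | 0 | Visit 6 − Visit 5 = 3m |
| 4 | 6 | 0 | Visit 7 − Visit 6 = 3m |

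The literal rule does not reproduce the 3-month length in any window. Closing minus opening visit reproduces it in all four. It also equals the number of days from the opening visit up to but excluding the closing visit, so no extra day is needed.

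**Effect in window 1.** The inflation factor is 3m / m = 3 for any month length. Illustration with assumed rates and m = 28:

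- True SSF 4 over 84 days: 4 × 84 / 28 = 12 seizures.
- SSF with the 84-day denominator: 12 / 84 × 28 = 4.
- SSF with the literal 28-day denominator: 12 / 28 × 28 = 12.
- Assumed baseline SSF 10. True change: (4 − 10) / 10 = −60%, a responder. Literal change: (12 − 10) / 10 = +20%, a non-responder.
- To count as a responder under the literal rule, a true reduction r must satisfy 3(1 − r) ≤ 0.5, so r ≥ 1 − 0.5 / 3 = 83%.

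With visits at days 30 and 91 the factor is 91 / 30 = 3.03, the same subject reads 0.4 × 3.03 − 1 = +21%, and the responder threshold is 1 − 0.5 / 3.03 = 83.5%.

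**Effect in windows 2 to 4.** The divisor is 0, so SSF, percent change and responder status are undefined.

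**Where the conflict does not reach.** The baseline period is named by both of its bounding visits (Visit 1 to Visit 2 of the parent study), so its denominator is well defined. The 1-week, 1-month and overall summaries are not among the windows bounded in section 6.1.

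**The case against.** The best reply is that the intended rule can be recovered. The windows are called 3-month windows, which a 1-month or 0-day denominator contradicts. The same formula is said to serve baseline, where first and last visit are plainly the bounding visits. Section 5.2.1 has seizures since the previous visit recorded at each return visit, so the closing visit is where the window's data are collected. An upper bound that excludes the closing visit is also a natural way to assign a seizure dated on a visit day to one window only. All of this stands, and it makes closing minus opening visit the likely intention.

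It is also fair that zero divisors in three of four windows would probably be noticed in programming and lead back to window 1. A reader might infer from the arithmetic that reported window 1 frequencies will be tripled and responders lost. The documents do not support that: it requires keeping the literal rule in window 1 after it has failed in the other three.

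A reader might also extend the excluded closing visit to the whole year, giving 9 months instead of 12 and a factor of 12 / 9 = 1.33. This has no basis in the text. Sections 5.2.1 and 5.2.2, item 7, run the year from Visit 1 to Visit 7, and the bounds in section 6.1 belong to the four windows only.

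Finally, an unscheduled or early-termination visit inside a window gives a non-zero literal value, so the zeros are not universal. That does not help the plan: some subjects who leave early would then be computable in windows where those who continue are not.

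What the reply does not remove is the conflict. No sentence in the SAP lets the excluded visit supply the end date, and section 6.2 only takes days away.

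**Conclusion.** Wrong as written, for the four 3-month windows. With scheduled visits only, the two rules together give a denominator of about 1 month in window 1 and 0 days in windows 2 to 4. Taken literally, and with visits on schedule, window 1 SSF is overstated about threefold, its percent change is shifted towards an increase and responders are undercounted. In windows 2 to 4 all three quantities are undefined. The threefold figure and the percentages derived from it describe the literal rule. They are not an expected bias, because the likely intention is recoverable.

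The endpoints are secondary and descriptive, in an open-label extension whose primary objective is safety. The conflict should still be resolved in the text, since the SAP's introduction presents it as the detailed statement of the analysis rules.

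**What to change.** In SAP section 5.2.2, item 2, state that for each 3-month window days on study is the date of the visit that closes the window minus the date of the visit that opens it: Visit 4 − Visit 1, Visit 5 − Visit 4, Visit 6 − Visit 5 and Visit 7 − Visit 6. For a subject who drops out within a window, the last available diary date replaces the closing visit. Days with missing diary data are then subtracted, as section 6.2 requires. Seizures are counted from the opening visit date up to but excluding the closing visit date, so that numerator and denominator cover the same days.

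The bounds in section 6.1 can stay as they are. The cost is a sentence or two of text. No new data are needed and there is no analytic downside.

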### **6.2 Handling of Dropouts or Missing Data**

Subjects who dropped out before study completion are not to be replaced and all available information obtained from them will be included in the appropriate efficacy

and safety summaries to the time of dropout. No imputation is planned for any safety measures.

If the date of the seizure is missing or incomplete and the seizure cannot be allocated to a study interval, these data will not be used in the analysis, but will be presented in the subject data listings. If the seizure diary was returned and there was no seizure data available for a particular day during that evaluation period, it will be assumed that the patient had missing seizure data, and the day will be excluded from the calculation of the standardized seizure frequency.

Seizure related variables will be calculated based on available data. For dropout subjects, their seizure frequency will be derived for each interval up to the last interval where the subject had data. The last interval standardized seizure frequency will be computed based on available data prior to dropout.

For QOLIE31 and MADRS, if only one item is missing, it will be imputed by the average of other items for calculating the total score (See Section 5.2.4: 1 and 2).

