## 5.2. Efficacy Assessment and Endpoints

### 5.2.1. Assessments

Each subject will be instructed to keep a seizure diary and record information on all seizures for the first one-year of the study starting from Visit 1 (Screening) and ending at Visit 7. Subjects or caregivers can complete the study diary; however the person who maintains the diary should remain the same throughout the study. Seizure occurrences since the previous visit, based on review of the seizure diary, will be recorded by date and seizure type on the eCRF. At return visits 2 through 7, the seizure diary will be reviewed, and collected.

The 31-Item Quality of Life in Epilepsy Scale (QOLIE-31) will be self-administered by only subjects who have completed 18 years of age at time of signing informed consent in Protocols 093-045 or 093-046.

The Montgomery-Asberg Depression Rating Scale (MADRS) measures the severity of a subject's depressive symptoms. MADRS will be performed by a credentialed and trained MADRS rater.

The Patient Global Impression (PGI) scale measures the patient impression of improvement in disease. The PGI will be subject self-administered at all visits during the Post-1-Year Open-Label Period only. The 5 individual items will be summarized with descriptive statistics for each Post-1-Year Open-Label Period visit.

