**5. Seizure-free**

Subjects who did not have any seizure as per the seizure diary during that time period will be deemed seizure free, for the corresponding interval of interest. However, subjects who discontinue prior to Visit 7 will be considered not seizure-free for the interval when the discontinuation takes place and all subsequent intervals (even if the subjects are seizure-free at the time of discontinuation). That is, subjects must complete each interval of interest without any seizures to be considered seizure-free for each interval of interest.

The number and percent of seizure-free subjects will be presented for the interval of interest, for each interval the percent will be based out of the number of subjects in the ITT population entering each interval of interest.

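### A reported seizure that cannot be allocated to an interval is left out of all analysis, so a subject with a known seizure can be tabulated as seizure-free

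*SAP*

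**What the plan says.** SAP section 6.2 sets two joint conditions, "If the date of the seizure is missing or incomplete and the seizure cannot be allocated to a study interval", and then the consequence: "these data will not be used in the analysis, but will be presented in the subject data listings".

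The outcomes that depend on this rule are defined in SAP section 5.2.2:

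- **Seizure freedom (item 5).** "Subjects who did not have any seizure as per the seizure diary during that time period will be deemed seizure free". The item has one conservative provision, and it is for dropouts: "subjects who discontinue prior to Visit 7 will be considered not seizure-free for the interval when the discontinuation takes place", and for every later interval.
- **SSF (item 2).** The numerator is "Total number of seizures reported in the diary during the interval of interest". The denominator is the span between the first and last visit dates of the interval. The same formula serves for baseline.
- **Relative change and responder status (items 3 and 4).** Both are derived from SSF.

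On data capture, SAP section 5.2.1 says: "Seizure occurrences since the previous visit, based on review of the seizure diary, will be recorded by date and seizure type on the eCRF". Diaries are reviewed and collected at Visits 2 to 7. Section 6.1 cuts the four 3-month windows at Visits 4, 5, 6 and 7. Section 7.6 reports the seizure outcomes at 1 week, at 1 month, by 3-month window and overall.

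**The concern.** An unknown date does not make it uncertain that the seizure happened. A seizure entered in a diary kept between Visit 1 and Visit 7 falls in the 1-year period even if its 3-month window is unknown. Section 6.2 nevertheless takes it out of the analysis without exempting the overall interval.

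Seizure freedom is all-or-none, so one omitted seizure can change a subject's classification. The SAP is strict elsewhere: a dropout with no recorded seizure counts as not seizure-free. Under the same plan, a completer with a recorded seizure could count as seizure-free.

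This is a single-arm, open-label extension, so no control group shares the error, and the proportion is reported with a 95% confidence interval. Maintenance of effect is a secondary objective. The efficacy summaries are descriptive, so no type I error or power is involved.

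**Working it through.** The plan gives no rate, count or sample-size calculation on this point, so there is no figure to reproduce. The check applies the SAP's own formula, SSF = 28 × n / D, with n seizures in D days. All values of n and D below are assumed.

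**1. Effect on an on-treatment interval.** Dropping one of n seizures changes SSF from 28n/D to 28(n − 1)/D, a relative change of −1/n.

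| n | Change in SSF |
|---|---|
| 1 | −100% |
| 2 | −50% |
| 5 | −20% |
| 14 | −7.1% |
| 40 | −2.5% |

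Section 6.2 also says that when a returned diary has no seizure data for a day, "the day will be excluded from the calculation of the standardized seizure frequency". If the dropped seizure's day is removed in this way, SSF becomes 28(n − 1)/(D − 1). With D = 91 the change is −49.4% for n = 2 and −6.1% for n = 14, so SSF is still too low.

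**2. The only seizure cannot be allocated (n = 1, D = 91).**
- Under the plan: SSF = 0, a 100% decrease, seizure-free.
- With the seizure counted: SSF = 28 × 1/91 = 0.31, not seizure-free.

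**3. Responder threshold (baseline SSF 8, D = 91, 14 seizures, one not allocable).**
- Under the plan: 28 × 13/91 = 4.00, a change of −50.0%, responder.
- With the seizure counted: 28 × 14/91 = 4.31, a change of −46.2%, non-responder.

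**4. The opposite direction, through baseline.** Assume a 56-day baseline with 16 seizures (SSF 8.0) and 13 on-treatment seizures in 91 days (SSF 4.0). The change is −50.0%. If the rule drops one baseline seizure, baseline SSF is 28 × 15/56 = 7.5 and the change becomes (4.0 − 7.5)/7.5 = −46.7%. A responder is lost.

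**5. The opposite direction, through blank days.** With three seizures in 91 days, true SSF is 28 × 3/91 = 0.923. With one dropped, it is 28 × 2/91 = 0.615. If 31 blank days are also excluded, it is 28 × 2/60 = 0.933, slightly above the true value. The net SSF bias across both rules therefore has no fixed sign. Excluding blank days does nothing to correct seizure-free status.

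**6. Seizure-free rate, illustration only.** Take N = 348, the sample size in the Protocol's summary of Amendment 3, which is a planned number and not the ITT count. Assume 35 subjects truly seizure-free, 35/348 = 10.1%, and m completers whose only seizures cannot be allocated. The reported rate is (35 + m)/348.

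| Assumed share affected | m | Reported rate |
|---|---|---|
| 0% | 0 | 10.1% |
| 0.5% | 2 | 10.6% |
| 1% | 3 | 10.9% |
| 2% | 7 | 12.1% |
| 3% | 10 | 12.9% |

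With the seizures counted, the rate is 10.1% in every row.

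**The case against.** The strongest reply is that the rule is narrow. An incomplete date excludes nothing by itself; the seizure must also be impossible to allocate. Seizures are recorded visit by visit since the previous visit, and the windows end at visits where diaries are collected. A diary collected at Visit 2, 3 or 4 points to the first window, and diaries from Visits 5, 6 and 7 point to the other three. Section 6.2 does not forbid allocation on that basis, and if it is done few seizures remain to be dropped. This stands, and it limits the likely size. It does not close the gap, because the SAP never says how allocation is made. A programmer who left out every seizure whose partial date does not fix the window could claim to have followed section 6.2.

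A second reply is that an undated diary entry is still a seizure according to the diary, and that the overall period is an interval to which it can be allocated. That is a sensible reading, but section 6.2 excludes such data from the analysis without exception, and the SAP does not say which section governs.

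A third reply concerns direction. A reader might infer that every seizure outcome is biased towards benefit. The documents do not support that: steps 4 and 5 show that a dropped baseline seizure or the blank-day rule can push the other way.

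Finally, the excluded seizures stay visible in the listings, and these are descriptive secondary outcomes in a safety extension. That is true and keeps the point minor, but a table that disagrees with its own listing is still wrong.

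**Conclusion.** The point holds as a minor defect with a simple remedy. As written, section 6.2 lets a subject with a known seizure in the 1-year period be tabulated as seizure-free with SSF 0, and nothing else in the SAP prevents it. The error runs one way for seizure freedom and for the on-treatment SSF numerator. For percent change, responder status and net SSF the direction is not fixed.

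The size is unknown. The range of 10.1% to 12.9% rests wholly on assumed values: 10.1% truly seizure-free, 0% to 3% of subjects affected, and the planned 348 as denominator. A reader might take the 2% row as showing that the rate is overstated by a fifth (7/35 = 20%). The documents give no basis for 2% or any other frequency, and diary collection at six visits suggests that the true figure is near the low end.

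**What to change.** Add to SAP section 6.2:

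1. A seizure with a missing or partial date is allocated to the interval ending at the visit where its diary was collected.
2. If it still cannot be placed in a 3-month window, it is counted in the overall 1-year SSF and the subject is classed as not seizure-free overall.

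Add a cross-reference in section 5.2.2, item 5, so that the seizure-free definition and the missing-date rule agree.

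Classing the subject as not seizure-free in every window the seizure might belong to should be at most a sensitivity analysis, since one seizure could then count against up to four windows.

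The cost is a few lines of SAP text and some programming, with no new data. The overall seizure-free rate may become slightly less favourable. A diary handed in late could place a seizure in a later window than the true one, but the overall result would not be affected.

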**4. Responder rate**

Responder is defined as having a ≥50% reduction in SSF from baseline.

The proportion will be calculated as the number of responders divided by the total number of subjects in the ITT population entering the period of interest.

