### **Seizure standard frequency (SSF)**

Descriptive statistics will summarize the SSF for 1 week, 1 month, each 3 month visit window of time, overall, and by the following subgroups: number of baseline AEDs,

and baseline AED medications, and seizure type.

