**Relative (%) change from baseline in SSF**

Relative (%) change from baseline in SSF will be summarized descriptively for 1 week, 1 month, each 3-month visit window, overall, and by the following subgroups: number of baseline AEDs, and baseline AED medications, seizure type. The number and percentage of subjects with the category in Section 5.2.2 will also be presented.

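### By-window SSF and percent change follow a shrinking cohort: if poorer responders leave more often, the trend over the year will look better than the true course

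*SAP*

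**What the plan says.** SAP 6.1 (3-month visit windows) divides the first year: "There are four 3-month intervals for the 1-Year Open-Label Period". SAP 6.2 sets the data rule: "Seizure related variables will be calculated based on available data". For subjects who leave it adds "For dropout subjects, their seizure frequency will be derived for each interval up to the last interval where the subject had data", and, for the part-window at the end, "The last interval standardized seizure frequency will be computed based on available data prior to dropout".

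SAP 7.6 applies this to two continuous measures. For SSF: "Descriptive statistics will summarize the SSF for 1 week, 1 month, each 3 month visit window of time, overall". For percent change: "Relative (%) change from baseline in SSF will be summarized descriptively for 1 week, 1 month, each 3-month visit window, overall". Both are descriptive, with subgroup repeats.

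For these two measures the SAP plans no fixed-cohort display, no imputation after dropout, no longitudinal model and no other sensitivity analysis for dropout. The per-protocol population (7.1) is defined by protocol deviations and the actual-monotherapy subgroup (6.5) by AED use, so neither holds the cohort constant over time. The responder rate in 5.2.2 is "divided by the total number of subjects in the ITT population entering the period of interest", so its denominator shrinks as well.

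**The concern.** Maintenance of effect over the year is a secondary objective (SAP 2.2), and readers will naturally compare window 1 with window 4. The two rows describe different people. The difference between them mixes change within subjects with change in who is left.

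The SAP makes it plausible that leaving is related to seizure control. Section 3.1 discontinues subjects who need more than two additional AEDs, and AEDs are added for a clinically significant worsening of seizures. Section 5.2.2 (item 8) counts withdrawal for lack of efficacy and, for the retention endpoint only, assigns several other withdrawal reasons to lack of efficacy. If poorer responders do leave faster, the later rows are selected towards good control. The trend then reads as maintained or improving when true control is flat, and may read as flat when true control is getting worse.

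**Working it through.** The documents state no dropout rate, effect size or power for this study, so there is no planned figure to reproduce. The check asks how far the window rows move when each subject's true seizure rate is held constant. Any movement is then an artefact.

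**Step 1. Two-group arithmetic.** Assume 40% of subjects have a 70% reduction and 60% a 10% reduction, with per-window dropout d_R and d_N respectively. Three dropout steps separate window 1 from window 4:

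mean in window 4 = [0.4(1 - d_R)³(-70) + 0.6(1 - d_N)³(-10)] / [0.4(1 - d_R)³ + 0.6(1 - d_N)³]

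- Window 1: 0.4 × (-70) + 0.6 × (-10) = -34.0%.
- Equal dropout (10% and 10%): the factors cancel, giving -34.0%.
- d_N = 10%, d_R = 5%: (0.34295 × (-70) + 0.4374 × (-10)) / 0.78035 = -36.4%.
- d_N = 15%, d_R = 5%: (0.34295 × (-70) + 0.368475 × (-10)) / 0.711425 = -38.9%.
- Reversed, d_N = 5%, d_R = 10%: (0.2916 × (-70) + 0.514425 × (-10)) / 0.806025 = -31.7%. The drift changes sign if the better responders leave faster.

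**Step 2. Simulation of the planned median.** Assumed inputs: 400,000 subjects; lognormal baseline SSF with median about 8 and a floor of 4; a constant true ratio to baseline with median 0.6 and log-SD 0.7; Poisson counts over 91 days. Dropout after each window depends on whether the true reduction is below 50% (poorer) or not (better). The better share is Φ(ln(0.5/0.6)/0.7) = 0.397, so the fraction reaching window 4 is 0.603(1 - d_N)³ + 0.397(1 - d_R)³.

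| Dropout per window, poorer v better | Median % change, window 1 | Window 4 | Reaching window 4 |
|---|---|---|---|
| 10% v 10% | -40 | -40 | 73% |
| 8% v 5% | -40 | -42 | 81% |
| 10% v 5% | -40 | -44 | 78% |
| 15% v 5% | -40 | -46 | 71% |
| 25% v 3% | -40 | -54 | 62% |

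The overall row, which keeps each leaver's data, has a median of about -40% in every line.

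A second model made dropout logistic in the true log ratio (N = 348, base risk 5% or 10% per window). It gave the same direction: window 4 at -44 to -55 for slopes of 0.5 to 1.5 per SD, and -40 at slope zero.

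**Step 3. Can a real loss be hidden?** Let every true rate rise 5% per window. The median ratio in window 4 is 0.6 × 1.05³ = 0.695, so the full cohort worsens from -40% to about -31%. With 15% v 5% dropout the planned rows go only from -40 to -38.5. With 25% v 3% they improve, to about -47.

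**Step 4. Does a fixed cohort help?** For subjects with data in all four windows, at 15% v 5%, the row is flat under constant rates (-46 to -46). Under the 5% loss it shows the deterioration (-46 to -38.5).

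**The case against.** The strongest reply is that the plan is descriptive and promises no trend claim. The primary objective is safety and tolerability. Section 5.2.2 lists eight one-year efficacy endpoints without ranking them, and time on monotherapy comes first. A reader might infer that the by-window rows are the plan's main evidence of maintenance; the documents do not say so.

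Nor is selective loss concealed. Retention time counts lack-of-efficacy and adverse-event withdrawals as events. Completion rates carry confidence intervals, disposition is given with reasons, and every continuous summary reports its number of subjects (6.1). Seizure-free status counts a leaver as a failure in the window of leaving. These outputs show that subjects left, but none separates within-subject change from selection in the SSF rows.

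The mechanism may also be weak. Section 3.1 lets poorer responders stay with dose changes and up to two added AEDs, which also makes constant individual rates a simplification. Withdrawals for adverse events among good responders could offset the drift or reverse it. This stands: the size, and even the presence, of the artefact depends on rates the documents do not give.

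Finally, carrying the last SSF forward is not a clean cure. Under 6.2 that value may rest on a few days: 3 seizures in 5 days becomes 3/5 × 28 = 16.8 per 28 days, then held for the rest of the year. This also stands.

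**Conclusion.** The point holds in conditional form. The SSF and percent-change rows by window are computed on a changing cohort with nothing planned to separate selection from within-subject change. If poorer responders leave more often, the trend is biased towards better control: by about 2 to 4 points on the median by window 4 for modest differences in dropout (8% or 10% v 5%), 6 points at 15% v 5%, and 14 points at 25% v 3%. It is zero if dropout is unrelated to response. These sizes rest on assumed dropout rates and an assumed response distribution.

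Two stronger readings are tempting and not supported. One is that the tables will show a false improvement: the documents give neither dropout rates nor their relation to response. The other is that the one-year seizure results as a whole are biased in this way: the overall summary keeps leavers' data and stays at about -40% in every constant-rate scenario. The problem is confined to comparisons between windows within the 1-Year Open-Label Period, the only period with diary data.

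**What to change.** In SAP 7.6, beside the planned SSF and percent-change rows, add the same by-window summary restricted to subjects with data in all four 3-month windows. State that any description of change over time within the 1-Year Open-Label Period will be read against that table. Say also whether a part-observed fourth window qualifies a subject, since 6.2 gives such a subject an SSF for it.

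The cost is a few lines of SAP text and one repeat table; no new data are needed. The limitation should be stated with it: the table describes those who stayed, so it shows within-subject trend and not the level of control in the full ITT population. Carrying the last-window SSF forward need not be required. If the sponsor wants it, it should be an optional sensitivity analysis, labelled as such.
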